### **4.3 Follow-up period**

Assessments during the Follow-up period will be carried out according to the schedule provided in [Table 1](#).

After patients complete the 8-week Treatment Phase-2, all cardiac loop recording and non-standard of care blood draws will stop.

As part of the Follow-up, patients will be seen by the electrophysiologist (EP) cardiologist (or qualified implanter) for removal of the LINQ device unless they decide to leave it implanted. All equipment including the Care monitor recording device will be returned to the Sponsor.

For each patient, removal of the LINQ device marks the study completion (the end of their study participation).

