**Table 1 Study Plan and Schedule of Assessments**

Study Period / Visit	Screening	ILR Insertion by EP cardiologist	Baseline/ Randomization	New Dialysate Accommodation Period 1	Treatment Phase 1	Cross-over	New Dialysate Accommodation Period 2	Treatment Phase 2	ILR Removal by EP cardiologist	End of Study	Reference to Protocol Section
Study Week (Wk) [* , ** or ***]	-4 to -3**	-2*	1**	1 & 2**	3 to 10**	11**	11 & 12**	13 to 20**	21-22*	22-23***	
Study Day (D)	-28 to -15	-14	1	1 to 14	15 to 70	71	71 to 84	85 to 140	Between D141 and D155	Within 1 to 14 days after ILR Removal	
Day of the week			M/T	M/T	M/T	M/T	M/T	M/T			
Written informed consent	X										4.1.1
Assignment of unique Screening Number	X										4.1.2
Demographics	X										4.1.3
Medical/surgical & Medication history	X										4.1.4
Physical examination	X										4.1.5
Vital signs and weight measurements	X			X	X		X	X		X	4.1.6
12-lead ECG	X										5.2.3.1
K+ Piccolo POCT (pre-dialysis) [1]	X			X	X		X	X			4.1.7 4.2.1

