### **6.4 Recording of adverse events**

#### **6.4.1 Time period for collection of adverse events**

Adverse events will be collected from the time of first dose of Lokelma®, throughout the treatment and post-treatment follow-up period, up to the last study visit.

SAEs will be reported from the time the patient signed the Informed Consent Form.

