#### **8.5.6 Safety Analyses**

Lokelma-induced hypokalemia will be evaluated based on the total number of hypokalemic events defined as PiccoloPOCT or laboratory-measured K+ of < 3.5 mEq/L.

The incidence of dialysis-related hypokalemia, hypomagnesemia, hypophosphatemia, and low calcium will be evaluated based on the number of events promptly prior to the termination of dialysis where a PiccoloPOCT measurement of K+ is < 2.0 mEq/L OR Ca++ is < 7.0 mEq/L, OR Mg++ is < 2.0 mg/dl, OR a PO4 level is < 3.0 mEq/L. All episodes where a specific electrolyte falls below the above listed threshold will be considered an “event” for that electrolyte. The total number of “events” will be recorded during the 8-week Treatment Phase-1 and the 8-week Treatment Phase-2 cross-over periods and compared between the treatments.

Safety will also be assessed in terms of the frequency of AEs, SAEs, and withdrawals due to AEs, with focus on treatment-related events. Appropriate summaries of these data will be presented by treatment group and/or study period.

Adverse events will be coded using the Medical Dictionary for Regulatory Activities (MedDRA) system organ class (SOC) and preferred term (PT). A treatment-emergent AE

(TEAE) is defined as an AE with the start date on or after the first dose date and up to (and including) 14 days after the last dose date in each of study periods when patients received 3K Bath with Lokelma. However, when patients received 2K Bath without Lokelma, A treatment-emergent AE (TEAE) is defined as an AE with the start date on or after the first visit date and up to (and including) 14 days after the last visit date in each of study periods. Only TEAEs will be included in table summaries.

The number and percentage of participants experiencing AEs, SAEs, AEs that led to withdrawal, AEs that led to death, and the number of such events, will be summarised by SOC, PT, and treatment group and study period. The number and percentage of participants experiencing AEs will further be summarised by intensity and will be presented with the number of events at each level of intensity.

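### Section 4.3 ends participation at loop-recorder removal, Table 1 schedules an End of Study visit after it, and neither guarantees the protocol's own 14-day adverse-event window after Phase 2

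*Protocol*

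**What the plan says.** Section 4.3 opens by referring follow-up to Table 1: "Assessments during the Follow-up period will be carried out according to the schedule provided in" that table. It then says patients see the electrophysiologist "for removal of the LINQ device unless they decide to leave it implanted", and closes by stating that for each patient "removal of the LINQ device marks the study completion (the end of their study participation".

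Table 1 has separate columns for removal and for End of Study. Treatment Phase 2 ends on D140. Removal is "Between D141 and D155", on any day. End of Study is "Within 1 to 14 days after ILR Removal" in the Study Day row and Weeks 22-23 in the Study Week row, and its footnote requires a dialysis day. The End of Study column carries vital signs, AE review, SAE review and concomitant medication.

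Section 6.4.1 and Table 1 footnote 8 collect adverse events "throughout the treatment and post-treatment follow-up period, up to the last study visit". Section 8.5.6 counts an event as treatment-emergent up to and including 14 days after the last dose in a 3.0 K period with Lokelma. For a 2.0 K period it counts events "up to (and including) 14 days after the last visit date in each of study periods".

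Exclusion criteria 18 and 21 in Section 3.2 allow patients whose existing recorder has enough battery life, so devices that stay in place are foreseeable.

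**The concern.** A patient cannot both leave the study at removal and attend a study visit after it. Because AE collection stops at the last study visit, the choice between the two statements decides when safety data stop.

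Both Section 4.3 and the Study Day row key the end of follow-up to a procedure date, not to the end of treatment. A patient whose recorder is removed promptly can leave collection well before the treatment-emergent window closes. A patient who keeps the recorder has no defined completion under Section 4.3 and no End of Study date under the Day row.

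Safety Objective #3 compares AE frequencies between the treatments, so incomplete collection after Phase 2 bears on a stated objective. Complications of the removal itself could also go unrecorded; Section 1.3 names chest-wall infection as a risk of insertion.

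**Working it through.** **Inputs.** Phase 2 is D85-D140, removal D141-D155, and End of Study is removal + 1 to + 14 days or Weeks 22-23 (Table 1). The End of Study visit must fall on a dialysis day (Table 1 footnote). Lokelma is taken on off-dialysis days (Section 7.2.1). The treatment-emergent window is 14 days (Section 8.5.6). Day 1 is a Monday for Mon-Wed-Fri patients and a Tuesday for Tue-Thu-Sat patients (Table 1).

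**Week and day labels.** With week = floor((day − 1)/7) + 1, Table 1's treatment labels reproduce: D1-14 = Weeks 1-2, D15-70 = 3-10, D71-84 = 11-12, D85-140 = 13-20. The End of Study label does not:

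- Day row: earliest 141 + 1 = D142, latest 155 + 14 = D169, which is Weeks 21-25.
- Week row: Weeks 22-23 are D(7 × 21 + 1) = D148 to D(7 × 23) = D161.

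**Weekdays.** D141 is 20 whole weeks after Day 1, so it is a Monday or a Tuesday. Then:

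- D140 is a Sunday or a Monday, a dosing day on both schedules, so the last planned dose is D140.
- D142 is a Tuesday or a Wednesday, off-dialysis on both schedules. The earliest Day-row visit is therefore D143.
- The last weekly Monday/Tuesday visit of Phase 2 is 85 + 7 × 7 = D134.

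**Windows to be covered.** Lokelma: 140 + 14 = D154. The 2.0 K bath: 134 + 14 = D148, assuming that the last visit date means the D134 weekly visit.

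**Earliest end of AE collection on each reading:**

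| Reading | Earliest end | Days after D140 | Lokelma days unobserved (154 − end) | 2.0 K days unobserved (148 − end) |
|---|---|---|---|---|
| Section 4.3, removal on D141 | D141 | 1 | 13 | 7 |
| Table 1 Day row with dialysis-day footnote | D143 | 3 | 11 | 5 |
| Table 1 Week row | D148 | 8 | 6 | 0 |

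**How much of the Day row is affected.** Before applying the dialysis-day rule, the row permits 15 removal days × 14 offsets = 210 combinations. Of these, 12 + 11 + … + 1 = 78 put the visit before D154. This counts what is permitted and is not a probability.

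**Length of participation from D-28.** To removal: (28 + 141)/7 = 24.1 to (28 + 155)/7 = 26.1 weeks, centred on the approximately 25 weeks in the synopsis. To the End of Study visit: (28 + 142)/7 = 24.3 to (28 + 169)/7 = 28.1 weeks.

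**The case against.** The best defence is that one stray sentence in Section 4.3 should not override the rest. The same section defers to Table 1, which marks AE and SAE review both at removal and at End of Study. Section 6.4.1 explicitly includes post-treatment follow-up, and Section 6.4.2 follows events unresolved at the last visit. On that reading safety follow-up exists, and the Week row keeps it at 8 days or more after D140. The two header rows can even be applied together: every permitted removal day leaves an End of Study date that satisfies both, the earliest being D148.

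Much of this stands. A reader might infer that there is no safety follow-up, or no observation at all after removal; the documents do not support that. Nor do they support saying that patients who keep the device have no End of Study visit, because the Week row gives dates that do not depend on removal. A visit on D142 is ruled out by the dialysis-day footnote.

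A reader might also infer that the window is complete after Phase 1, so that only Phase 2 is deficient. That is not secure. Section 6.4.1 starts AE collection at the first Lokelma dose, which for patients on the 2.0 K bath first comes after cross-over at D71, whereas Table 1 marks AE recording from the first accommodation period. The post-Phase 1 window also overlaps exposure to the other treatment.

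The defence does not remove the contradiction in Section 4.3. It also leaves the Lokelma window up to 6 days short on the most favourable reading, and nothing says which header row governs.

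**Conclusion.** The point holds as an inconsistency with a bounded consequence. Section 4.3 and Table 1 disagree on when participation ends. Table 1's rows give different ranges. Section 4.3 and the Day row have no anchor for patients who keep the device. As a result the 14-day window of Section 8.5.6 is not guaranteed after Phase 2: at worst 13, 11 or 6 Lokelma days and 7, 5 or 0 days on the 2.0 K bath go unobserved, depending on the reading.

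These are the earliest permitted dates, not expected ones; the documents give no distribution of removal dates. The Lokelma figures assume a last dose on D140 as planned; an earlier last dose shortens the window. The 2.0 K figures assume D134 as the last visit; a later one lengthens the shortfall day for day.

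It would be too strong to conclude that the treatment comparison is biased. Each treatment comes second in one of two sequences randomized 1:1, and safety is reported descriptively, so any loss mainly separates Phase 2 from Phase 1. It is not exactly balanced, because the window is anchored to the last dose for one treatment and to the last visit for the other. On the Week row, for example, only the Lokelma window can be cut short. The matter should be corrected, but it does not threaten the primary analysis.

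**What to change.** - Delete the sentence in Section 4.3 that ends participation at removal. State that the Table 1 End of Study visit ends participation for every patient, whether or not the device is removed. Section 6.4.1 then needs only to name that visit as the last study visit.
- Anchor the visit to the end of treatment and reconcile the Week and Day rows. D154 is off-dialysis on both schedules (a Sunday or a Monday), so the first dialysis day after the window is D155. Schedule the visit on a dialysis day from D155, after removal if removal occurs, and no later than the D169 that the Day row already permits.
- Define which visit is the last visit date for a 2.0 K period in Section 8.5.6.

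The cost is wording in Section 4.3, the Table 1 header, Section 6.4.1 and Section 8.5.6. The visit stays on a dialysis day, so it needs no extra attendance. Some patients remain in the study somewhat longer: D-28 to D155 is (28 + 155)/7 = 26.1 weeks. The stated approximately 25 weeks should be revised, although the latest date already permitted (D169, 28.1 weeks) does not move.

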## **5. STUDY ASSESSMENTS**

The Investigators will ensure that data are recorded on the eCRFs as specified in the study protocol and in accordance with the instructions provided.

The Investigators are responsible for the accuracy, completeness, and timeliness of the data recorded and of the answers to data queries according to the Research Agreement. The Investigator will sign the completed eCRFs. A copy of the completed eCRFs will be archived at the study site.

### **5.1 Efficacy Assessments**

#### **5.1.1 Atrial Fibrillation**

As described in [Section 2.1](#), the primary objective of this study is to determine whether increasing the K+ concentration in a standard hemodialysis bath from 2.0 K+/2.5 Ca++ to a 3.0 K+/2.5 Ca++ composition with Lokelma will reduce the incidence of atrial fibrillation events.

Atrial fibrillation will be defined as irregular heart rhythms and irregular R-R intervals in the absence of definable P waves for a minimum of 6 minutes.

Atrial fibrillation events will be detected, recorded, and stored by the Medtronic LINQ device; see [Section 4.1.8](#). This data will be downloaded on a weekly basis during both 8-week treatment periods (Treatment Phase-1 and Treatment Phase-2); see [Section 4.2.2](#) for details.

Each atrial fibrillation event will be adjudicated and validated as a true atrial fibrillation event centrally by cardiologist who will be blinded to the treatment assignment.t.

### 5.1.2 Clinically Significant Cardiac Arrhythmias

As detailed in [Section 2.2](#), the frequency and duration of post-dialysis CSCAs (defined as bradycardia, ventricular tachycardia and/or asystole) observed during experimental treatment compared to standard treatment will be evaluated as part of the secondary endpoints of the study.

CSCA events will be defined as follows:

- Bradycardia: Heart rate of  $\leq 40$  beats per minute (BPM) for a minimum duration of 6 seconds.
- Ventricular Tachycardia: Regular tachy-arrhythmia of  $\geq 130$  BPM for a minimum duration of 30 seconds
- Asystole: Absence of detectable ventricular conduction for a minimum of 3 seconds.

The occurrence of these typically silent arrhythmias will be detected, recorded, and stored by the Medtronic LINQ device; see description of the device in [Section 4.1.8](#). Patients “sensing” a cardiac arrhythmia during dialysis will “mark” the event with the LINQ marking device. This data will be downloaded on a weekly basis during both 8-week treatment periods (Treatment Phase-1 and Treatment Phase-2); see [Section 4.2.2](#) for details. Upon concluding that a cardiac arrhythmia is occurring, the dialysis technician will draw a Green Top and Tiger Red Top tubes from the dialysis line as the dialysis is being terminated.

All “patient marked” events will be adjudicated centrally by the reviewing cardiologist and reported to the Site PI if it considered that immediate attention is required.

### 5.1.3 Potassium Measurements

A further secondary objective of the study (see [Section 2.2](#)) is to determine whether the addition of oral sodium zirconium cyclosilicate (Lokelma®) during the 2-month treatment phase with the 3.0 K+/2.5 Ca++ dialysate bath will reduce the number of days outside the “K+ safety range” of 4.0 to 5.5 mEq/L compared to the 2-month treatment phase with the 2.0 K+/2.5 Ca++ dialysate bath.

K+ Piccolo POCT will be performed weekly during the two 8-week Treatment phases, as follows: pre-dialysis, and promptly before dialysis termination and 30 minutes prior to rinse back (along with Ca++ and PO4 measurements); see [Section 4.2.1](#).

### 5.1.4 Correlations Between Laboratory Parameters and Clinical Events

The study will also evaluate the correlation between PBUTs (PCS, indoxyl sulfate, and ADMA) and the frequency of atrial fibrillation events, as well as the correlation between electrolyte levels and clinical events (intradialytic hypotension, muscle cramping, and cardiac arrhythmias); see [Section 2.4](#).

Measurements of PBUTs and electrolytes are described in [Section 4.2.1](#). The recording and assessment of cardiac arrhythmias are detailed in [Section 4.2.2](#) and [Section 5.1.2](#), respectively.

The occurrence of other clinical events (intradialytic hypotension, muscle cramping) will be recorded during dialysis throughout the two 8-week treatment periods.

Intradialytic hypotension is defined as a systolic blood pressure (SBP) < 90 mmHg and any of the following events:

- A requirement to reduce the ultrafiltration rate
- A requirement for administration of a saline bolus
- Development of altered sensorium or level of alertness
- Onset of shortness of breath (SOB) or angina-like symptoms.

Muscle cramping is defined as any episode of painful muscle spasm that prompts the patient to alert the Dialysis staff of his/her discomfort.

## 5.2 Safety assessments

### 5.2.1 Laboratory safety assessments

Blood samples for determination of select clinical chemistry parameters will be collected and analyzed as indicated in the Study Plan (see [Table 1](#)).

As part of the safety objectives of the study, the number of hypokalemic events defined as Piccolo POCT or laboratory-measured  $K^+$  of < 3.5 mEq/L, and the number of events of pre- or post-dialysis  $Ca^{++}$  < 2.5  $Ca^{++}$  mEq/L,  $PO_4$  levels <3.0 mEq/L and  $Mg^{++}$  < 2.0 mg/dL will be evaluated and compared between the two treatments (experimental vs standard); see [Section 2.3](#).

All Piccolo POCT measurements will be completed locally. The Piccolo POCT device and methodology are described in [Section 8](#), and the blood draws, including sample tubes and volumes collected are detailed in [Section 4.2.1](#). In addition, the following laboratory variables will be measured at the site as part of the Piccolo POCT renal panel:

**Table 2**                      **Piccolo Renal Function Panel**

---

Sodium (Na + )
Potassium (K + )
Phosphorus (PHOS)
Blood urea nitrogen (BUN)
Calcium (Ca ++ )
Albumin (ALB)
Glucose (GLU)

Creatinine (CRE)

Estimated Glomerular Filtration Rate (eGFR)

Chloride (Cl)

---

The Investigator should make an assessment of the available results with regard to clinically relevant abnormalities. For information on how AEs based on laboratory tests should be recorded and reported, see [Section 6.4.6](#).

### **5.2.2 Physical examination**

As described in [Section 4.1.5](#), at screening (prior to the placement of the implantable loop recorder), patients will undergo a complete physical examination that will focus on general appearance, respiratory and cardiovascular systems, and lower extremities, and will include a limited neurological exam. No subsequent physical exams will be mandated.

### **5.2.3 Cardiac Monitoring**

In this study, continuous cardiac recordings will be performed as part of efficacy evaluations throughout the two 8-week treatment phases, using the Medtronic insertable loop recorder (ILR, LINQ device). Insertion of the cardiac loop recorder is described in [Section 4.1.8](#). Cardiac data recordings are detailed in [Section 4.2.2](#).

#### **5.2.3.1 12-lead ECG**

As indicated in [Section 4.1.7](#), Standard resting 12-lead ECG recording will be performed at Screening only and used for confirmation of eligibility.

### **5.2.4 Vital signs**

As indicated in [Section 4.1.6](#), measurement of vitals is standard of care throughout each dialysis session, and will include blood pressure, pulse, and body temperature.

For information on how AEs based on vital signs measurements should be recorded and reported, see [Section 6.4.6](#).

### **5.2.5 Other safety assessments – Concomitant Medications**

All concomitant medications taken by the subject from the time of their consent signature will be recorded; see [Section 7.7](#).

### **5.2.6 Pregnancy Test for Females of Childbearing Potential**

As indicated in [Section 4.1.4](#), a pregnancy test should be performed during screening for females of childbearing potential to confirm eligibility.

## **5.3 Safety Protocols**

### **5.3.1 Safety Protocol for Patients with Piccolo POCT-Confirmed Hypokalemia or Hyperkalemia**

Hyperkalaemia will be defined as a  $K^+ \geq 7.0$  mEq/L and measured using Piccolo POCT technology in pre-dialysis obtained after the long dialysis “weekend”. Unless clinically unstable, patients with hyperkalaemia will be dialyzed and managed according to the judgment of the Site PI. Dose adjustments of Lokelma will be with each patient prior to discharge.

Hypokalemia is defined as pre-dialysis  $K^+$  level of  $< 3.5$  mEq/L. Patients experiencing a minimum of two (2) hypokalemic events while taking Lokelma will have their Lokelma adjusted or discontinued at the discretion of the site PI.

Patients with clinically significant cardiac arrhythmias including bradycardia, ventricular tachycardia, and asystole that are recognized by the dialysis staff during an individual dialysis session will be managed according to site unit protocols and include necessary resuscitation and transfer to the nearest emergency department.

### **5.3.2 Safety Protocol for Patients with Intra-Dialytic Arrhythmias**

Patients developing clinically apparent dialysis-associated arrhythmia including atrial fibrillation with or without with rapid ventricular response (RVR), atrial tachycardia (defined as sustained pulse  $>130$  bpm), bradycardia (defined a symptomatic pulse of  $< 40$  bpm) will be sent to the nearest emergency department for treatment at the discretion of the PI. All such events will be marked by the LINQ marking device.

If a complete metabolic panel is performed as standard of care, the results will be recorded in the patient’s source chart and electronic data capture system (EDC).

### **5.3.3 Safety Protocol for Patients with Intra-Dialytic Hypotensive Events**

All patients with a dialysis-associated hypotensive event (defined as a systolic blood pressure  $<90$  mmHg) will be managed according to standard site unit protocols that may include:

- a) The termination of all ultrafiltration
- b) Administering a 500 ml saline bolus
- c) Documenting the presence of altered sensorium or level of alertness
- d) Documenting the presence of shortness of breath (SOB) or angina-like symptoms

All patients “sensing” a cardiac arrhythmia during dialysis will “mark” the event with the LINQ marking device.

If a complete metabolic panel is performed as standard of care, the results will be recorded in the patient’s source chart and EDC.

Note: Should the patient quickly revive with the above listed maneuvers and the Site PI assesses that the patient can continue dialysis, the patient can complete their dialysis session.

### **5.3.4 Safety Protocol for Patients with Intra-Dialytic Symptomatic Muscle Cramping**

A “symptomatic episode of muscle cramping” is defined as an event associated with any of the following:

- a) Requirement to lower the dialysis ultrafiltration rate
- b) Requirement for a saline bolus
- c) Patient request to terminate dialysis (whether the dialysis session is stopped or not)
- d) Decision to terminate dialysis.

Patient management during each of the above clinical scenarios will be left to the discretion of the site PI or according to existing protocols within the participating dialysis unit.

Upon onset of a “cramping event” the dialysis technician will follow typical dialysis unit protocols including reducing the ultrafiltration rate and giving a saline bolus. At this point the dialysis nurse or technician will draw a 5.0 ml Yellow Top SST tube from the dialysis line prior to the termination of the dialysis session, to be sent to the dialysis local lab for Mg++ and PO4 levels (if possible).

All patients developing an episode of “symptomatic muscle cramping will “mark” the event with the LINQ marking device.

